### **Overview and Objective**

A person's genetic code is believed to affect how much weight he/she will lose during diets that vary in carbohydrate and dietary fat content. 'Carbohydrate responders' are hypothesized to lose more weight on diets that are high in carbohydrates, as compared to high in fats. 'Fat responders' are hypothesized to lose more weight on diets that are high in dietary fat, as compared to high in carbohydrates. The purpose of the proposed study is to test these hypotheses in a randomized controlled trial.

### **Background**

Obesity and its comorbidities are major public health challenges. To combat the obesity pandemic, many weight-loss strategies have been studied, often emphasizing either high carbohydrate (low fat) diets or high fat (low carbohydrate) diets. Mean weight loss differences between high-carbohydrate and high-fat diets that induce equal caloric deficits have been reported to be small; however, the individual weight loss response varies substantially within diet groups, suggesting that different individuals react differently to high-carbohydrate or high-fat diets. This assumption is supported by retrospective data showing that participants with carbohydrate-responsive polymorphisms lost 2-3 times more weight when assigned to a high-carbohydrate diet compared to a high-fat diet, and vice versa for those with dietary fat-responsive polymorphisms. Conversely, a recent randomized clinical trial aimed to determine the effect of a healthy high-fat diet (high in unsaturated fats) vs. a healthy high-carbohydrate diet (high in whole-grain foods) on 12-month weight change but did not find significant differences between the two groups and failed to find the hypothesized association between genotype patterns and weight loss induced by diets that varied in fat and carbohydrate content. However, an important caveat of their approach is that the single nucleotide polymorphisms selected by the investigators had not been previously associated with obesity or with dietary response, which may explain their lack of predictive value in identifying differences in inter-individual responses. In addition, the fat composition of the diets was relatively high in both high- and low-fat groups. The inconsistent findings in the literature indicate a need for further research to determine if genetic factors affect weight loss when exposed to diets that vary in carbohydrates and dietary fats.

The purpose of this randomized controlled parallel arm trial is to test the following hypotheses.

**Hypothesis 1** will test if participants assigned to the diet that corresponds to their genotype lose more weight than those assigned to a diet inconsistent with their genotype.

**Hypothesis 2** will analyze the fat responders and carbohydrate responders separately.

- **Hypothesis 2a:** Fat responders will lose more weight on the high-fat diet vs. the high-carbohydrate diet.

- **Hypothesis 2b:** Carbohydrate responders will lose more weight on the high-carbohydrate diet vs. the high-fat diet.

Carbohydrate and dietary fat responders will be identified *a priori* based on their combined genotypes at pre-determined genetic variants using specific algorithms. Carbohydrate responders and fat responders will be randomized to one of the following two diets:

1. A high-quality high-carbohydrate diet that is rich in whole-grain foods, or
2. A high-quality high-fat diet that is rich in unsaturated fats and oils (Table 1).

**Table 1.** Overview of the study design and expected relative weight loss (double arrows reflect greater expected weight loss). The total number per group is an estimate. We will not close cells to enroll this exact number per group, and the total number of people enrolled will not exceed 154.

	High-Fat Diet	High-Carb Diet
Fat Responder	Cell A n=52 ↓↓	Cell B n=52 ↓
Carb Responder	Cell C n=25 ↓	Cell D n=25 ↓↓

Both diets will last 12 weeks and have the same levels of protein (15% of energy). The high-carbohydrate diet will consist of ~20% of energy from fat and ~65% from carbohydrates. The high-fat diet will consist of ~40% energy from fat and ~45% from carbohydrates. All participants will be assigned an energy intake target that will result in a daily deficit of ~750 kcal, though no energy intake targets below 1,100 kcal/d (women) and 1,300 kcal/day (men) will be prescribed. At the discretion of the PI or MI, modest diet modifications will be allowed if needed for participant safety. Baseline energy requirements will be calculated with the formulas of Mifflin St. Jeor. The Remote Food Photography Method (RFPM) and SmartIntake smartphone app will be used sporadically as needed to facilitate dietary adherence. These are process data and will not be immediately analyzed to quantify dietary intake, though the images can be fully analyzed later. Rather, the food images will be reviewed by the interventionists in near real-time to help the participant select and eat foods consistent with their meal plan.

The dietary program and intervention materials will be developed and delivered by employees of Pennington Biomedical Research Center (PBRC). Outcome assessors will be blind to diet assignment and genotype pattern. Interventionists will be blind to genotype pattern, but not diet type. To enhance internal validity, participants will not be told if they are carbohydrate or fat responders until after they complete the study. The **primary outcome** variables are weight change (kg and %) over 12 weeks. All other measures are secondary endpoints. The schedule of procedures is provided in **Table 2**.

**Table 2.** Schedule of visits and procedures.

	Orientation	Baseline (Week 0)	Week 6**	Week 12
Location	IBL	Clinic	IBL	Clinic
Consent, eligibility, demographics, medical history form	X			
Height	X			
Weight	X	X	X	X
Genealogy test kit	X			
Waist/hip circumference, bioelectrical impedance analysis, blood pressure, heart rate, Food Craving Inventory, Food Preference Questionnaire, Eating Inventory		X		X
Blood draw: fasting serum glucose, insulin		X		
Randomization		X		
Intervention Satisfaction Survey				X
Diet Personalization Survey (completed after randomization and at week 6 and 12)		X	X	X
* There is no clinic visit at week 6. The week 6 weight will be collected at the participants' intervention visit, where participants will also complete the Diet Personalization Survey. If participants miss this visit, they will complete the Diet Personalization Survey during the next intervention visit.				
** Weight will be collected at each of the 12 intervention visits.				

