### **Data analytic plan**

The biostatistics department will handle the randomization and use adaptive randomization to promote equal numbers of men and women in each cell and to promote similar BMI across the groups.

The primary outcome variable is body weight change, represented as kg and percent change. All other variables are secondary and will be analyzed using a similar statistical approach. Repeated mixed linear models will be used to determine if change in the outcome variables differs among the groups. Covariates will include the baseline value of the outcome, sex, and race. Additional variable selection in the models will be determined through model fit statistics such as AIC.

Two sources of body weight data are obtained – weights collected in the clinic at baseline and week 12, and weights collected at the 12 intervention sessions. Both sources of data will be analyzed, though the presence of only two clinic weights means that analysis of the clinic weights will be a completers' analysis. The weekly weight data, however, will be analyzed using an intent-to-treat approach, and all participants' data will be analyzed who have a weight from their first and at least one subsequent intervention visit. Sensitivity analysis will be conducted to determine how the two methods effects the results.

The primary models will be a mixed effect model that accounts for the correlation of the subject over time modeling. Least square means based on the estimates from the mixed effect model will be used to test for differences of weight change between groups. Normality of the responses will be checked based on the Shapiro-Wilk test. Heterogeneity of variance effects for genders for each of the treatments will be analyzed first as potential subgroups.

Hypothesis 1 will test if participants assigned to the diet that corresponded to their genotype lost more weight than those assigned to a diet inconsistent with their genotype.

- H1: Weight loss in Cells A and D (combined) in Table 1 was significantly larger than weight loss in Cells B and C (combined).

Hypothesis 2 will analyze the fat responders and carbohydrate responders separately.

- H2a: Fat responders lost more weight on the high-fat diet (Table 1, Cell A) vs. the high-carbohydrate diet (Cell B), and
- H2b: Carbohydrate responders lost more weight on the high-carbohydrate diet (Table 1, Cell D) vs. the high-fat diet (Cell C).

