#### Orientation Visit: About 1 hour.

The orientation visit will take place at Pennington Biomedical Research Center and it will include the following procedures:

- Informed consent
- Questionnaires assessing medical history, current medication and supplement use, and demographics
- Measurement of height and weight
- If participants have completed a genealogy test before the study, their data will be reviewed to verify eligibility to participate in the study
- If participants have NOT completed a genealogy test before the study, they will be provided with a genealogy test kit and the data will be reviewed as soon as they are available to us to determine eligibility to participate in the study

Baseline Clinic Visit: About 1.5 hours.

If participants are eligible and wish to participate in the study, the first clinic visit will be scheduled. The visit will take place in the Outpatient Clinic of Pennington Biomedical Research Center. *This is a fasting visit (nothing to eat or drink before the visit, following a 12-hour fast).* The clinic visit will include the following procedures:

- Measurement of waist/hip circumference
- Bioelectrical impedance analysis (weight and body fat %)
- Measurement of blood pressure and heart rate
- Completion of the following self-report instruments: Food Craving Inventory, Food Preference Questionnaire, Eating Inventory
- Fasting serum glucose and insulin (no archiving)
- If participants will be using their own scale for at home weights during intervention, they will be asked to bring the scale in for calibration.

Weekly Intervention Visits (approximately 1.5 hours per visit)

The 12 weekly intervention visits will take place at Pennington Biomedical Research Center or virtually and they are designed to be specific to participants' random assignment, i.e., either the high-fat or the high-carbohydrate diet group. Body weight will be recorded by study staff at each of these 12 intervention visits. Additionally, participants will regularly weigh themselves at home (approximately once per day) and they will turn in a record of these self-measured weights at each weekly intervention visit. Participants will either be provided a loaner scale to use during the intervention or they will use their at home scale, calibrated by study staff at the Baseline visit.

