The first intervention visit will be a one-on-one in person or virtual meeting with the interventionist following the baseline visit where participants will complete the Diet Personalization Survey. The next 11 intervention visits will be in person or virtual group meetings with other participants and a facilitator. The facilitator is a Pennington Biomedical Research Center staff member. Participants will receive personalized meal plans that are tailored to their calorie and (group-dependent) macronutrient target and they will include precise portion sizes of daily meals and snacks, a shopping list, and restaurant options. Two snacks per day (e.g., granola bar) will be provided by the sponsor, WW. The sponsor will further provide a food scale for each participant to facilitate adherence to the prescribed portion sizes.

Discussions and content delivered during the sessions will focus on helping participants adhere to their assigned diet. At the week 6 intervention visit, the Diet Personalization Survey will be completed.

Week 12 Clinic Visit: About 1.5 hours.

The visit will take place in the Outpatient Clinic at Pennington Biomedical Research Center. *This is a non-fasting visit.*

The visit will include the following procedures:

- Measurement of weight and waist/hip circumference
- Bioelectrical impedance analysis (weight and body fat %)
- Measurement of blood pressure and heart rate
- Completion of the following self-report instruments: Food Craving Inventory, Food Preference Questionnaire, Eating Inventory, Intervention Satisfaction Survey, Diet Personalization Survey
- If participants were loaned a scale for intervention, they will be asked to return it at this visit.

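### The first Diet Personalization Survey is completed after randomisation, so using it as a baseline can bias the between-diet comparison of that survey, usually towards zero

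*Combined protocol and SAP*

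**What the plan says.** Table 2 (Background) lists the survey as "Diet Personalization Survey (completed after randomization and at week 6 and 12" and marks it in the Baseline (Week 0), Week 6 and Week 12 columns. Under Study Procedures, Weekly Intervention Visits, the first visit is a "one-on-one in person or virtual meeting with the interventionist following the baseline visit where participants will complete the Diet Personalization Survey". The survey is not among the baseline clinic procedures listed in the same section. Of the intervention visits the protocol says that "they are designed to be specific to participants' random assignment, i.e., either the high-fat or the high-carbohydrate diet group", and of the staff who lead them, "Interventionists will be blind to genotype pattern, but not diet type".

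On endpoints, Background states: "All other measures are secondary endpoints". On analysis, the Data analytic plan states: "All other variables are secondary and will be analyzed using a similar statistical approach". That approach is a repeated mixed linear model for change in the outcome, and "Covariates will include the baseline value of the outcome, sex, and race". No exception is written for any instrument. The same section applies a Holm-Bonferroni adjustment to these other variables and promises the sponsor tables of values at every assessment visit as well as tables of change.

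**The concern.** Adjusting for a baseline value is safe because randomisation makes that value independent of assignment. The first survey lacks this protection. By the time it is completed, the participant has been randomised and is attending a diet-specific session with someone who knows the diet. The answers may already be a response to the assignment.

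If so, using that score as the starting point for change, or as a covariate, conditions on part of the effect being estimated. A diet difference that appears early and persists would be understated in the inferential results at weeks 6 and 12. At stake is the interpretation of one secondary measure.

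**Working it through.** **Timing.** Three statements together show that no pre-randomisation score exists: the note in Table 2, the placement of the first survey at the first intervention visit, and its absence from the baseline clinic list. The other repeated measures (weight, waist and hip, bioelectrical impedance, blood pressure, heart rate and the three eating questionnaires) are scheduled at the baseline clinic visit. The Intervention Satisfaction Survey is given at week 12 only.

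**Plan's own figure.** There is none for this survey, so nothing can be reproduced. What follows depends on assumptions.

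**Inputs**
- From Table 1: 52 + 25 = 77 participants per diet. The protocol calls the cell sizes estimates.
- Assumed: D, the week-12 diet effect, is 0.5 SD; f, the share of D present at the first survey, runs from 0 to 1; rho, the within-group correlation between first and week-12 scores, runs from 0.3 to 0.7. Variances are equal, so the within-group slope equals rho.

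**Formulas.** The diet difference is f × D at the first survey and D at week 12.
- Unadjusted change: D − fD = D(1 − f).
- Week-12 score adjusted for the first score: D − rho × fD = D(1 − rho × f).
- Change adjusted for the first score: the slope on the first score is rho − 1, so the estimate is (D − fD) − (rho − 1)fD = D(1 − rho × f), the same result.
- Week-12 score without the first score as covariate: D.

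**Estimates for D = 0.5 SD (share of the effect lost)**

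| f | Adjusted, rho 0.3 | Adjusted, rho 0.5 | Adjusted, rho 0.7 | Unadjusted change |
|---|---|---|---|---|
| 0 | 0.50 (0%) | 0.50 (0%) | 0.50 (0%) | 0.50 (0%) |
| 0.25 | 0.46 (7.5%) | 0.44 (12.5%) | 0.41 (17.5%) | 0.375 (25%) |
| 0.5 | 0.425 (15%) | 0.375 (25%) | 0.325 (35%) | 0.25 (50%) |
| 1 | 0.35 (30%) | 0.25 (50%) | 0.15 (70%) | 0 (100%) |

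Simulation (77 per diet, 1,500 runs per setting) agreed with these values to within 0.01 SD.

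**Power in the same simulation** (two-sided alpha 0.05, no Holm step). Comparing week-12 scores without the first score gives about 0.87. The model adjusted for the first score gives, for rho 0.3, 0.5 and 0.7:
- f = 0: 0.90, 0.95, 0.99
- f = 0.5: 0.77, 0.76, 0.81
- f = 1: 0.59, 0.40, 0.25

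When f is small, the precision gained from the covariate can offset the attenuation in terms of power, but the estimate is still biased.

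**Direction.** The bias is towards zero when the early difference has the same sign as the later one. If the early difference had the opposite sign (f negative), the same formula would inflate the effect.

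**The case against.** The strongest reply is that the plan promises only a similar approach, and that some adaptation is unavoidable: the satisfaction survey has no baseline, and glucose and insulin have no follow-up. Nor does the plan name the first survey as its own baseline value. A survey about an assigned diet may make sense only after assignment, and change from the start of the diet may be the question of interest. The first survey also comes at the first of 12 visits, so f may be small.

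Much of this stands. The timing may well be deliberate and is not criticised here; f could be near zero, in which case nothing is lost. But the wording does not settle the matter. Unlike the satisfaction survey, this one has an entry in the Baseline column, so the covariate rule applies to it directly unless an exception is written.

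A reader might infer more than the documents support:
- **That the plan removes the diet effect.** The planned model includes the first score as covariate and attenuates by rho × f. Complete removal needs unadjusted change with f = 1, or rho × f = 1.
- **That the matched-versus-mismatched contrast is equally exposed.** Participants do not learn their responder type until they finish, interventionists are blind to it, and there has been little or no time on the diet. The documents offer little route to an early difference on that contrast.
- **That a sustained difference would be hidden.** Values at each visit will be tabulated; it is the inferential result that may be attenuated.
- **That the survey is meant to detect a diet effect.** The documents give no content, scoring or hypothesis for it.

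**Conclusion.** The point holds as a minor one. The only score that could serve as a baseline for the Diet Personalization Survey is obtained after randomisation, and the general rule for secondary outcomes would use it as reference and covariate. The resulting bias in the between-diet comparison ranges from none, if the diet has not yet affected the first score, to a loss of 30% to 70%, if the whole week-12 effect is already present and rho lies between 0.3 and 0.7. These sizes rest on assumed f and rho and on equal variances; the documents give no data to narrow them. Weight, Hypotheses 1 and 2, and the other instruments are untouched.

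**What to change.** Add to the Data analytic plan that the three Diet Personalization Survey scores are all post-randomisation outcomes and are exempt from the baseline-covariate rule. Analyse them in a repeated-measures model with group, time and group-by-time, adjusted only for pre-randomisation covariates such as sex, race and BMI, and report the group difference at each of the three times. Do not constrain the groups to a common mean at the first survey. Do not rely on the group-by-time term alone, since it again tests change. Change from the first survey can be reported as descriptive.

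This takes a sentence or two and no new data. The cost is some precision if the diet has not affected the first score: in the f = 0 setting above, power is about 0.87 instead of 0.90 to 0.99.

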### Pilot Participants

Before the start of the study, we will conduct a trial run of the process of determining the genetic risk score from the Ancestry.com, 23andMe, and GeneticDirection raw data. We will recruit up to 6 volunteers who either: 1) have the raw data from 23andMe or Ancestry.com and are willing to share these data with us, or 2) are willing to complete 23andMe or Ancestry.com, or GeneticDirection testing (paid for by the study/PBRC) and share the raw data with us to determine their genetic risk score. These pilot participants will receive their genetic risk score but will not receive weight-loss treatment, though they are eligible to screen for, and possibly enroll in, the main trial. These participants will meet the same inclusion and exclusion criteria as those for the main study.

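### Pilot volunteers receive their genetic risk score and may then enrol in the main trial, which conflicts with the rule that participants do not learn their responder type until they finish.

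*Combined protocol and SAP*

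**What the plan says.** The design text under Background sets a masking rule and gives its purpose: "To enhance internal validity, participants will not be told" their responder type until they have completed the study. The item on the genealogy companies under Risks to Subjects is consistent with this, since participants get the login to their genealogy accounts only after the study is over.

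The Pilot Participants section describes a rehearsal of the scoring: "Before the start of the study, we will conduct a trial run of the process of determining the genetic risk score". It covers a handful of people ("We will recruit up to 6 volunteers who either" hold raw genetic data already or agree to be tested). It then states: "These pilot participants will receive their genetic risk score but will not receive weight-loss treatment". In the same sentence it adds that "they are eligible to screen for, and possibly enroll in, the main trial". On eligibility it says: "These participants will meet the same inclusion and exclusion criteria as those for the main study".

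The Exclusion Criteria do not mention people who already know their score. The Data analytic plan neither flags pilot enrollees nor provides an analysis without them.

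**The concern.** The contrast in Hypothesis 1 is matched against mismatched diet, and Hypotheses 2a and 2b test the same contrast within each responder type. Participants necessarily know their diet, because they follow diet-specific meal plans. Withholding responder type is therefore what keeps them from knowing whether they are matched.

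Someone who can work out their type from a returned score loses that protection. A person who believes they are matched may adhere better. A person who believes they are mismatched may adhere less well or leave. Both responses favour the study hypothesis. The clinic-weight analysis is a completers' analysis, so it would not recover a difference in dropout. The carbohydrate-responder cells are the most exposed, because Table 1 plans only 25 people in each.

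**Working it through.** **Comparison of the text.** The masking rule covers participants in general and ends at study completion. The pilot section provides for return of the score and permits later enrolment. Both can be honoured only if the score is held back from those who enrol, or if those who have it do not enrol. The plan states neither condition.

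**Inputs.**
- Maximum pilot size: 6 (Pilot Participants).
- Cells of 52, 52, 25 and 25, total 154 (Table 1). Each side of Hypothesis 1 has 52 + 25 = 77.
- Planned difference 2.0 kg, SD 2.8 kg, alpha 0.05 (Power analysis).
- Estimated population split: one third fat responders, one third carbohydrate responders, one third neither or either (Inclusion Criteria).
- Shift in weight change from knowing one's match status, *b*: 0 to 2 kg. This is an assumption. The upper end equals the whole planned difference.

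**Share affected, at most.** 6/154 = 3.9% of the trial; 6/50 = 12% of carbohydrate responders.

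**Shift in a contrast.** With *k* such participants and *n* per side, the shift is *k* × *b* / *n*. Balanced allocation does not cancel it. If three matched people lose *b* kg more and three mismatched people lose *b* kg less, the difference moves by 3*b*/*n* + 3*b*/*n* = 6*b*/*n*, the same as six on one side.

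**How many might enrol.** On the plan's thirds, 6 × 2/3 = 4 would be eligible, 2 of them carbohydrate responders. If the same-criteria sentence means that all six are already responders, an equal split gives 3 carbohydrate responders. Full enrolment is assumed throughout; partial enrolment lowers every figure.

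| Contrast | *k* | *n* per side | Shift for *b* = 0 to 2 kg |
|---|---|---|---|
| Hypothesis 1 | 4 | 77 | 0 to 0.10 kg |
| Hypothesis 1, maximum | 6 | 77 | 0 to 0.16 kg |
| C vs D | 2 | 25 | 0 to 0.16 kg |
| C vs D | 3 | 25 | 0 to 0.24 kg |
| C vs D, maximum | 6 | 25 | 0 to 0.48 kg |

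Against 2.0 kg, 0.16 kg is 8% and 0.48 kg is 24%. The last row needs all six to be carbohydrate responders. On the plan's thirds that has probability (1/3)^6 = 0.14%; if all six are known to be responders in equal proportion, it is (1/2)^6 = 1.6%.

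**Power if six were left out of the analysis** (two-sample t-test, 2.0 kg, SD 2.8 kg, two-sided 0.05).
- Hypothesis 1: 0.993 (77 per side) to 0.991 (74 per side).
- A vs B: 0.950 to 0.938 (49 per side), if all six are fat responders.
- C vs D: 0.697 to 0.639 (22 per side), if all six are carbohydrate responders.

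The last two are extremes that cannot both occur. The plan does not say whether its tests are one- or two-sided. Its stated power of 0.80 is reproduced for C vs D only one-sided (0.801), so the two-sided values above start lower.

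**The case against.** A reader might infer that anyone who enrols from the pilot certainly knows their responder type before randomization. The documents do not go that far, for three reasons.

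1. The pilot section returns a genetic risk score, and does not say that the score names the type or comes with a cut-off. Type is assigned by algorithms applied to combined genotypes. Still, the pilot rehearses this scoring and no other classifier is described, so the inference is strong, though not literal.
2. The trial run is dated before the study, but the return of the score is not dated. Returning it after main-trial completion would satisfy both sections. The plan does not say that this will happen.
3. Enrolment is only a possibility, and responder status is generally unknown when volunteers are recruited, so some of the six may prove ineligible.

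A reader might also infer a material threat to the trial's conclusions. That would rest on the six-in-one-comparison figure and on a shift of 1 kg or more per person, for which the documents give no support. Hypothesis 1 barely moves even at the maximum.

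These objections limit both the certainty and the size of the problem. They do not remove the conflict, because the text as written permits the breach and contains nothing to prevent or detect it.

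**Conclusion.** The conflict is real and unresolved in the current text, and its likely effect is small. What is established is that the pilot section allows people who have received a genetic risk score into a trial whose own masking rule withholds responder type. That they could infer their type, and would have the score before enrolling, is a well-founded inference and not a stated fact.

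The size depends on the assumed 0 to 2 kg shift and on how many pilot volunteers enrol. At the expected count, the effect is at most 8% of the planned difference for Hypothesis 2b and about 5% for Hypothesis 1 (0.10/2.0). Only an improbable run of six carbohydrate responders would make it noticeable, and then only for Hypothesis 2b. This is a minor point, worth correcting because the correction is cheap and protects the contrast that the trial was set up to test.

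**What to change.** Amend the Pilot Participants section in one of two ways:

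- anyone who has received a pilot score is not eligible for the main trial, with a matching line in the Exclusion Criteria; or
- the pilot score is withheld until the person has completed the main trial or been found ineligible for it.

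If any pilot volunteer has already enrolled knowing their score, identify them in the dataset and repeat Hypotheses 1 and 2 without them as a sensitivity analysis, reported beside the main result.

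The first option costs at most six potential recruits. They can be replaced within the cap of 154, so planned power need not fall. The second costs only a delay in returning the score. The sensitivity analysis costs almost no power for Hypothesis 1. Its loss for Hypothesis 2b depends on how many of those removed are carbohydrate responders.
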